#### Part A

• Treatment 1: 25-mg OM oral solution

Subjects will be admitted to the research facility on Day -1 in Part A, at which time baseline procedures will be performed. After an overnight fast of at least 10 hours, subjects will be administered treatment with 250 mL of water. No food will be allowed for at least 4 hours postdose. Water is allowed as desired except for 1 hour before and after drug administration.

Subjects will stay at the research facility until Day 3. Pharmacokinetic (PK) samples will be collected to determine plasma OM concentrations. Subjects will be discharged after completion of Day 3 activities and will return for a safety follow-up visit on Day 6. PK results from Part A will be available prior to Part B. For subjects whose resulting Cmax in Part A is > 350 ng/mL, the Day 6 visit will be considered their end of study visit.

#### Part B

- Treatment A: Placebo oral solution
- Treatment B: 50-mg OM oral solution
- Treatment C: 400-mg moxifloxacin oral tablet

After completing Part A, eligible subjects will be randomized to receive 3 treatments in 1 of 6 sequences, as follows:

Sequence	Period 1	Period 2	Period 3
1	А	В	С
2	В	С	Α
3	С	Α	В
4	Α	С	В
5	С	В	Α
6	В	Α	С

Subjects will be admitted to the research facility on Day -1 of Period 1 in Part B. After an overnight fast of at least 10 hours, subjects will be administered treatment with 250 mL of water. No food will be allowed for at least 4 hours postdose. Water is allowed as desired except for 1 hour before and after drug administration. Placebo and OM treatments will be double-blinded and moxifloxacin treatment will be open-label. Subjects will receive standardized meals at approximately the same time.

Subjects will stay at the research facility throughout Part B, and study assessments will be performed according to the protocol, including continuous ECG recording, digital ECG extractions, and PK sample collections to determine plasma OM and moxifloxacin concentrations. Additionally, standard safety assessments, including 12-lead ECGs and vital signs monitoring, will be performed and safety and tolerability monitoring will be conducted throughout the study. Subjects will be discharged after completion of Day 6 activities in Period 3.

All study treatments will be separated by a washout period of at least 7 days (including between Part A and Part B).

# 4 Cardiodynamic ECG Assessment

## 4.1 ECG and PK Sample Collection

In Part B, continuous 12-lead digital ECG recording will be performed on Day 1 of each treatment period. The recording will be performed for approximately 27 hours in total. Subjects should lie down in a quiet room for at least 10 minutes before and 5 minutes after each extraction at the time points listed. Digital 12-lead ECGs will be extracted in up to 10 replicates at -1.25, -1, and -0.75 hours predose and at 0.25, 0.5, 0.75, 1, 1.5, 2, 3, 4, 8, 12, 24 hours postdose.

The Investigator site will utilize their Mortara Surveyor system. The continuous 12-lead digital ECG data will be stored onto SD memory cards. The ECGs to be used in the analyses will be read centrally by ERT.

The following principles will be followed in ERT's core laboratory:

• ECG analysts are blinded to the subject, visit, and treatment allocation.

• Baseline and on-treatment ECGs for a particular subject will be over-read on the same lead and will be analyzed by the same reader.

ECG intervals will be measured by the core laboratory in a blinded manner using the Expert Precision QT technique (see Appendix A for more details). The ECG database will be locked before any statistical analysis is undertaken.

Blood samples for PK determination will be drawn at the same time points as ECGs (i.e., predose and at 0.25, 0.5, 0.75, 1, 1.5, 2, 3, 4, 8, 12, 24 hours postdose) and additionally at 48, 72, 96, 120 hours postdose. PK samples should be collected within 5 minutes after the completion of the digital ECG extraction window through 24 hours postdose and within  $\pm$  2 hours of the digital ECG extraction windows after 24 hours postdose.

## 4.2 Study Objectives

### 4.2.1 Primary Objective

The primary objective of the study is to assess the effect of a single therapeutic (50 mg) oral dose of OM on the QT/QTc interval, relative to placebo, in healthy subjects.

### 4.2.2 Secondary Objectives

The secondary objectives are:

- To assess the PK of OM after a single oral dose to healthy subjects.
- To evaluate the effect of OM on other ECG parameters (heart rate [HR], PR and QRS intervals, and treatment-emergent T-wave abnormalities and presence of U waves).
- To determine the plasma concentration-effect relationship for OM on the QT/QTc interval in healthy subjects.
- To evaluate assay sensitivity by evaluation of the positive control, a single 400-mg oral dose of moxifloxacin, on the QT/QTc interval in healthy subjects.
- To evaluate the safety and tolerability of OM after a single oral dose to healthy subjects.

## 4.3 Cardiodynamic ECG and Endpoints

#### 4.3.1 Primary ECG Endpoint

The primary endpoint is the placebo-corrected change from baseline in QT interval corrected for HR based on the Fridericia correction (QTcF) interval ( $\Delta\Delta$ QTcF) after OM dosing.

#### 4.3.2 Secondary ECG Endpoints

The secondary endpoints are:

- ΔΔQTcF after moxifloxacin dosing
- Change-from-baseline HR, QTcF, PR and QRS intervals (ΔHR, ΔQTcF, ΔPR, and ΔQRS) after OM dosing

- Concentration-QTc analysis based on ΔΔQTcF after OM dosing
- Placebo-corrected  $\Delta$ HR,  $\Delta$ PR, and  $\Delta$ QRS ( $\Delta\Delta$ HR,  $\Delta\Delta$ PR, and  $\Delta\Delta$ QRS) after OM dosing
- Categorical outliers for QTcF, HR, PR, and QRS after OM dosing
- Frequency of treatment-emergent changes in T-wave morphology and U-wave presence after OM dosing

#### 5 Statistical Methods

## 5.1 General Methodology

All statistical analyses will be performed using the statistical software SAS for Windows Version 9.4 or higher (SAS Institute, Inc., Cary, NC). Data collected from all randomized subjects will be presented in data listings. Both observed values and change-from-baseline values for each subject will be given where applicable. All continuous data will be listed with the same precision as will be presented in the database. Data listings will be sorted by subject ID, treatment, and time point. Missing values will be represented by an empty cell and no imputation will be made unless specifically stated otherwise.

Analysis Data Model (ADaM) datasets will be prepared using Clinical Data Interchange Standards Consortium (CDISC) ADaM Version 2.1 and CDISC ADaM Implementation Guide Version 1.1. Pinnacle 21 Community Validator Version 2.2.0 will be utilized to ensure compliance with CDISC standards.

Continuous data will be summarized using descriptive statistics including number of subjects (n), mean, median, standard deviation (SD), standard error (SE), 90% confidence interval (CI), minimum, and maximum by treatment and time point. Mean and median values will be rounded to the nearest tenth, or to the first non-zero decimal. SD, SE, and CI will be rounded to the nearest hundredth, or to 1 digit more than the nearest non-zero digit. For the concentration-QTc analysis, 3 significant digits will be kept for the effect estimates. *P* values will be reported with 4 digits and *P* values less than 0.0001 will be reported as < 0.0001. Percentages will be rounded up or down to the nearest tenths decimal place.

## 5.2 Analysis Populations

The analysis populations for cardiodynamic ECG assessment are defined as follows (Table 1).

Table 1 Analysis sets for cardiodynamic ECG assessment in Part B

Population	Definition
Full analysis set (FAS)	All randomized subjects who have received at least 1 dose of each study treatment (OM, moxifloxacin, and placebo).
PK analysis set	All subjects who received at least 1 dose of OM and have evaluable PK data. Any subject who experiences emesis within 4 hours of dosing or diarrhea within 24 hours of dosing may be excluded from the PK analysis.

Population	Definition
QT/QTc analysis set	All subjects in FAS with measurements at baseline as well as ontreatment with at least 1 postdose time point with a valid $\Delta QTcF$ value. The QT/QTc analysis set will be used for the by-time point and categorical analyses of cardiodynamic ECG parameters.
PK/QTc analysis set	All subjects who are in both the QT/QTc and PK analysis sets with at least 1 pair of postdose PK and QTcF data from the same time point as well as subjects in the QT/QTc analysis set who received placebo. The PK/QTc analysis set will be used for the concentration-QTc analysis in Part B.

## 5.4 QT Correction Methods

The QT and RR value for each beat will be used for HR correction. Twelve-lead ECGs will be extracted in up to 10 replicates from each nominal time point prespecified in the protocol. The median value of each parameter from the set of evaluable beats in each extracted replicate will be calculated, and then the mean of all available medians (minimum 3 medians) from the nominal time point will be used as the subject's reportable value at that time point.

The Fridericia's correction (QTcF) is defined as QTcF (ms) = QT (ms)/[RR (ms)/1000]1/3.

For evaluation of the HR-corrected QT interval, a scatter plot and quantile plot of QTcF and RR intervals by treatment with a regression line and a linear mixed-effects line (90% CI), respectively, also will be given.

# 6 Analysis

## 6.1 By-Time Point Analysis (Primary Analysis)

The primary analysis of the QT/QTc data will be the "by-time point" analysis for QTcF, based on a linear mixed-effects model with  $\Delta$ QTcF as the dependent variable; period, sequence, time (categorical), treatment (OM, moxifloxacin, and placebo), and time-by-treatment interaction as fixed effects; and baseline QTcF as a covariate. An unstructured covariance matrix will be specified for the repeated measures at time points for subject within treatment period. If the model with an unstructured covariance matrix fails to converge, other covariance matrices such as compound symmetry and autoregressive will be considered. The model will also include a subject-specific random effect. If the fixed effects for period and/or sequence should prove to be not significant (i.e., if the P value > 0.1), these effects may be

removed from the model and the analysis will be repeated without those covariates. From this analysis, the least squares (LS) mean, SE, and 2-sided 90% CI will be calculated for the contrast "OM versus placebo" at each postdose time point, separately. If the upper bound of the CI of  $\Delta\Delta$ QTcF lies below 10 ms for all postdose time points, OM will be concluded not to have a significant effect on QT interval prolongation.

The SAS code for the by-time point analysis for QTcF is as follows.

PROC MIXED DATA=ECG; CLASS SUBJID TREAT TIME PERIOD SEQUENCE; MODEL DQTC=BASE TREAT TIME TREAT\*TIME PERIOD SEQUENCE/DDFM=KR; random intercept / SUBJECT = SUBJID type=UN; REPEATED TIME / SUBJECT = PERIOD\*SUBJID type = un; LSMEANS TREAT\*TIME/CL DIFF ALPHA=0.1; RUN;

Where ECG=QT/QTc analysis set, SUBJID=subject identifier, TREAT=treatment (OM, moxifloxacin, and placebo), TIME=nominal time point, BASE= baseline QTcF, PERIOD=period, SEQUENCE=sequence, and DQTC=ΔQTcF.

## 6.1.1 Secondary By-time Point Analysis

For HR, PR, and QRS interval, the analysis will be based on the change from baseline post-dosing ( $\Delta$ HR,  $\Delta$ PR, and  $\Delta$ QRS). The same model will be used as described for QTcF in the by-time point analysis. The LS mean, SE, and 2-sided 90% CI from the statistical modeling for both change-from-baseline and placebo-corrected change-from-baseline values will be listed in tables and graphically displayed.

#### 6.1.2 Assay Sensitivity

The analysis to show assay sensitivity will be based on  $\Delta QTcF$  of moxifloxacin. The same model will be used as described for the primary analysis.

For the time points 2, 3, and 4 hours after dose administration, the contrast in treatment  $\Delta\Delta QTcF =$  "moxifloxacin – placebo" will be tested against the 1-sided null hypothesis  $\Delta\Delta QTcF \le 5$  ms at the 5% significance level. Multiplicity will be controlled using the Hochberg procedure. If after this procedure the lower bound of the 2-sided 90% CI for LS mean  $\Delta\Delta QTcF$  is significantly larger than 5 ms for at least 1 time point of these 3 time points, assay sensitivity will be considered shown. In addition, 2-sided 90% CIs will be obtained for the contrast at all time points and used in the figures.

## 6.2 Categorical Analysis (Secondary Analysis)

Results for categorical outliers, T-wave morphology, and U-wave presence will be summarized in frequency tables with counts and percentages for both number of subjects and number of time points. Subject data will be summarized using the count of distinct subjects that fall into the category and the percentage of the total number of subjects. Time point data will be summarized using the count of time points at which the assessments fall into the category and the percentage of the total number of time points at which assessments are performed. Counts (either number of subjects or number of time points) for each treatment will be used as the denominator in the calculation of percentages unless otherwise specified.

A subject or time point will be determined as an outlier if the following criteria (which are assessed separately) are met for the ECG intervals (Table 2).

Table 2 Criteria for determining a subject or time point outlier

ECG interval	Categorical outlier criteria	
QTcF	Treatment-emergent value of $> 450$ and $\le 480$ ms when not present at baseline (new onset)	
	Treatment-emergent value of $> 480$ and $\le 500$ ms when not present at baseline (new onset)	
	Treatment-emergent value of > 500 ms when not present at baseline (new onset)	
	Increase of QTcF from baseline of > 30 and ≤ 60 ms	
	Increase of QTcF from baseline > 60 ms	
PR	Increase of PR from baseline > 25% resulting in PR > 200 ms	
QRS	Increase of QRS from baseline > 25% resulting in QRS > 120 ms	
HR	Decrease of HR from baseline > 25% resulting in HR < 50 bpm	
	Increase of HR from baseline > 25% resulting in HR > 100 bpm	

All outliers will be summarized for each treatment on the basis of incidence rates. A subject will be counted only once for a particular outlier event if the subject experiences more than 1 episode of that event. The total number of time points will be based on the number of observed time points across all subjects within a treatment.

For T-wave morphology and U-wave presence, treatment-emergent changes will be assessed, i.e., changes not present at baseline. For each category of T-wave morphology and of U waves, the category will be deemed as present if observed in any replicates at the time point.

The T-wave morphology and U-wave presence categories are described as follows (Table 3).

Table 3 T-wave morphology and U-wave presence categories (assessed manually)

Category	Description	
Normal T-wave (+)	Any positive T-wave not meeting any criterion below.	
Flat T-wave	T-amplitude < 1 mm (either positive or negative), including flat isoelectric line.	
Notched T-wave (+)	Presence of notch(es) of at least 0.05 mV amplitude on ascending or descending arm of the positive T-wave.	
Biphasic	T-wave that contains a second component with an opposite phase that is at least 0.1 mV deep (both positive/negative and negative/positive and polyphasic T-waves included).	
Normal T-wave (-)	T-amplitude that is negative, without biphasic T-wave or notches.	
Notched T-wave (-)	Presence of notch(es) of at least 0.05 mV amplitude on descending or ascending arm of the negative T-wave.	
U waves	Presence of abnormal U waves.	

The number and percentage of subjects in each treatment having changes from baseline that represent the appearance of the morphological abnormality will be summarized. The total number of time points having a particular change category will be summarized in terms of number and percentage based on the number of observed time points across all subjects within a treatment.

## 6.3 Concentration-QTc Analysis (Secondary Analysis)

The relationship between OM plasma concentration and  $\Delta QTcF$  will be investigated by linear mixed-effects modeling with  $\Delta QTcF$  as the dependent variable, time-matched concentration of OM as the explanatory variable (0 for placebo), centered baseline QTcF (i.e., baseline QTcF for individual subject minus the population mean baseline QTcF for all subjects in the same period) as an additional covariate, study treatment (OM = 1 or placebo = 0) and time (i.e., postdose time point) as fixed effects, and a random intercept and slope per subject (Garnett et al²). In all calculations, concentrations in subjects who received placebo will be set to zero. OM plasma concentrations below the quantifiable limit at predose will be set to zero and after dosing will be set to 1/2 the lower limit of quantitation in the concentration-QTc analysis.

An unstructured covariance matrix will be specified for the random effects. If the model with an unstructured covariance matrix fails to converge even after appropriate rescaling of the concentrations, the random effect on the slope and intercept will be dropped, in this order, until convergence is achieved. If an unstructured covariance structure does not converge after rescaling and removing the random terms in the model, then other covariance matrices, such as compound symmetry and

autoregressive, will be considered until convergence is achieved. The degrees of freedom (*df*) estimates will be determined by the Kenward-Roger method. From the model, the slope (i.e., the regression parameter for the concentration) and the treatment effect-specific intercept (defined as the difference between active and placebo) will be estimated together with the 2-sided 90% CI. The estimates for the time effects will be reported with degrees of freedom and SE.

The geometric mean of the individual  $C_{max}$  values for subjects on the active dose group will be determined. The predicted population average  $\Delta\Delta QTcF$  (ie, slope estimate  $\times$  concentration + treatment effect-specific intercept) and its corresponding 2-sided 90% CI at this geometric mean  $C_{max}$  will be obtained.

The plot of the observed median-quantile OM concentrations and associated mean placebo-adjusted  $\Delta QTcF$  (i.e.,  $\Delta\Delta QTcF$ ) with 2-sided 90% CI together with the regression line presenting the predicted  $\Delta\Delta QTcF$  (2-sided 90% CI; as described by Tornøe et al) will be used to evaluate the adequacy of the model fit to the assumption of linearity and the impact on quantifying the concentration-QTc relationship. The observed  $\Delta QTcF$  values from the active group will be adjusted by the estimated time effect from the concentration-QTc model (i.e., the estimated diurnal effect under the placebo treatment). The individually estimated placebo-adjusted  $\Delta QTcF_{i,j}$  ( $\Delta\Delta QTcF_{i,j}$ ) equals the individual  $\Delta QTcF_{i,j}$  for subject i administered with OM at time point j minus the estimation of time effect at time point j. Additional plots will be used to validate the model assumptions. Exploratory analyses (via graphical displays and/or model fitting) will also include accounting for a delayed effect (hysteresis; Section 6.3.1) and the justification for the choice of pharmacodynamic model (linear versus nonlinear; Section 6.3.2).

The SAS code for the concentration-QTc analysis is as follows.

PROC MIXED DATA=PKPD method=reml; CLASS SUBJID TIME; MODEL DQTC=TRT CONC TIME CBASE/ solution cl noint alpha=0.1 alphap=0.1 COVB DDFM=KR; RANDOM INT CONC /type=UN SUBJECT=SUBJID s; ESTIMATE 'Pred Mean Diff for T1' TRT 1 CONC &GeoMeanCmax\_1 / CL ALPHA=0.1; RUN;

Where PKQTc =PK/QTc analysis set, SUBJID=subject identifier, TRT=treatment (active=1 or placebo=0), TIME=nominal time point, CONC=OM plasma concentration, CBASE=centered baseline QTcF, T1 = therapeutic oral dose of OM, GeoMeanCmax\_1=geometric mean  $C_{max}$  for T1, and DQTC= $\Delta$ QTcF.

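### The concentration-QTc fallback discards the between-subject slope before trying a simpler covariance; the primary model's fallback names no heterogeneous structure and sets no order

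*SAP*

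**What the plan says.** **Concentration-QTc model (SAP 6.3, secondary).** The starting point is a random intercept and slope per subject: "An unstructured covariance matrix will be specified for the random effects". If this does not converge after the concentrations are rescaled, "the random effect on the slope and intercept will be dropped, in this order, until convergence is achieved". The next step begins "If an unstructured covariance structure does not converge after rescaling and removing the random terms in the model, then other covariance matrices", naming compound symmetry and autoregressive as examples. The only covariance statement in the SAS code is "RANDOM INT CONC /type=UN SUBJECT=SUBJID s"; there is no REPEATED statement. Degrees of freedom are Kenward-Roger. Protocol 8.3.5 includes the same two random effects and gives no convergence rule.

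**Primary by-timepoint model (SAP 6.1; Protocol 8.3.3.2 has matching wording).** An unstructured matrix is planned for the timepoints within a subject's period, plus a random subject intercept. The fallback is: "If the model with an unstructured covariance matrix fails to converge, other covariance matrices such as compound symmetry and autoregressive will be considered". No order is given and no heterogeneous form is named. SAP 4.1 lists 11 postdose timepoints ("0.25, 0.5, 0.75, 1, 1.5, 2, 3, 4, 8, 12, 24 hours postdose"), and the upper bound must be below 10 ms at each of them.

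**The concern.** When an unstructured 2 x 2 matrix for intercept and slope fails, the usual first simplification is to set their covariance to zero and keep both variances. SAP 6.3 goes straight to deleting the slope. If subjects truly differ in slope, a model with an intercept only treats that variation as residual noise averaged over all observations, and the standard error of the predicted effect at Cmax comes out too small. Kenward-Roger adjusts degrees of freedom and small-sample variance under the fitted covariance; it does not repair a wrong covariance. The step that tries other matrices comes too late to help: with both random terms gone, the stated code leaves only independent residuals.

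The primary model has a related but weaker problem. In standard form, compound symmetry and AR(1) use one variance for every timepoint, while the decision is taken timepoint by timepoint. A timepoint that is noisier than average then gets too narrow an interval.

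The aim of the study is to exclude an effect, so an interval that is too narrow where the effect peaks matters.

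**Working it through.** **1. The plan's own power figure.** Inputs from SAP 6.4: n = 48, true difference 3 ms, margin 10 ms, one-sided 5%, within-subject SD 7 or 8 ms, 8 timepoints.
- SE = SD × √(2/48): 1.429 ms (SD 7) and 1.633 ms (SD 8).
- Power per timepoint = Φ(7/SE − 1.645): Φ(3.254) = 0.99943 and Φ(2.642) = 0.99587.
- To the 8th power (independent timepoints): 99.5% and 96.7% (96.4% with t on 94 df). The plan states 99.5% and 96.5%, so the figures reproduce. They use one SD for all timepoints.

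**2. Concentration-QTc: cost of dropping a real slope.** The documents give no variance components. Assumed: 48 subjects, OM and placebo, 11 timepoints, residual SD 6 ms, intercept SD 3 ms, slope SD 0.005 ms per ng/mL, prediction at 410 ng/mL. Protocol 1.3.3 expects a mean Cmax of about 440 ng/mL at 50 mg, so 410 is a plausible geometric mean.
- Slope variation at Cmax: 410 × 0.005 = 2.05 ms per subject.
- Variance left out of the mean: at least about 2.05²/48 = 0.088 ms².
- The intercept-only model reports an SE of 0.50 ms. Adding the missing part gives √(0.250 + 0.088) = 0.58 ms, so coverage is at best about 2Φ(1.645 × 0.50/0.58) − 1 = 84%.
- The intercept-and-slope model has a mean simulated SE of 0.62 ms: 2Φ(1.645 × 0.50/0.62) − 1 = 82%.
- Comparing reported with true SE analytically gives 83%. Direct simulation gives 76% (400 replicates, Monte Carlo SE 2 points) and 78% (60 replicates, SE 5 points).

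These calculations do not agree closely, so the result is a range of 76-83%. With other assumed SDs (residual 7, intercept 5, same slope SD) the SE ratio is 0.557/0.672 = 0.83 and coverage 83%.

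In the 60-replicate simulation, uncorrelated intercept and slope held 88-90%.

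**3. When would the slope be dropped?** As an imperfect proxy for a failed unstructured fit, count REML fits with the random-effects matrix on its boundary (residual SD 6, intercept SD 3, 400 replicates per setting):

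| True slope SD (ms per ng/mL) | Fits on boundary | Coverage, intercept only |
|---|---|---|
| 0 | 60% | 91% |
| 0.002 | 42% | 86% |
| 0.005 | about 10% | 76-83% (step 2) |
| 0.01 | 0 of 400 | about 62-69% |

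At 0.005, the 41 replicates on the boundary had coverage of about 73%, so the loss is also seen when the proxy is triggered.

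**4. Dropping the intercept too.** With no slope variation at all (residual 7, intercept 5), independent residuals give an SE of 0.646 ms against a true 0.741 ms: coverage 85% at Cmax, and 69% for the slope estimate. The intercept-only model, however, was never on its boundary in step 3 (0 of 400 in each setting).

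**5. Primary model: one pooled variance.** Coverage at a timepoint with SD s is 2Φ(c × pooled/s) − 1. Timepoint SDs are assumed.
- Pooled 7 ms, c = 1.661 (t, 94 df): s = 8 gives 85% and one-sided error 7.3%; s = 9 gives 80% and 9.8%.
- Two noisy timepoints entering the pool, c = 1.645: √((9×49 + 2×64)/11) = 7.19 gives 86% and 7.0%; √((9×49 + 2×81)/11) = 7.40 gives 82% and 8.8%.
- At the nine quieter timepoints, coverage rises to 90.9% or 91.8%: those intervals are slightly too wide.

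**The case against.** - **The fallback list for the primary model is open.** A reader might infer that SAP 6.1 forces one variance on all timepoints. It does not: the wording gives examples, so heterogeneous versions are permitted. What stands is that none is named and no order is set, which leaves the choice until after the data are seen.
- **Pooling cuts both ways.** It might seem that either fallback always favours a finding of no QT effect. For the primary model that is wrong: intervals widen at quieter timepoints, and the excess error arises only if the true effect reaches 10 ms at a noisy timepoint while the others pass.
- **The worst coverage figures do not match the trigger.** Coverage of 62-69% belongs to a slope SD of 0.01, where the unstructured fit was never on its boundary (0 of 400, and 0 of 60 in the smaller simulation). Fits are most often on the boundary when slope variance is near zero, where little is lost. This stands, and limits the concern to intermediate slope variation.
- **Treating a subject's 22 values (11 OM, 11 placebo) as independent is remote.** It needs the intercept-only model to fail as well. The later sentence could also be read as a residual covariance by subject, although the code does not show one.
- **Consequence is limited.** The concentration-QTc analysis is secondary and its prediction at Cmax has no pass/fail rule. Nothing in the documents shows that the planned fits will fail. Still, the primary unstructured matrix has 11 × 12/2 = 66 parameters plus a random intercept for about 48 subjects, and the SAP itself provides for failure.

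**Conclusion.** The point holds as a contingency, not as a fault in the planned models. SAP 6.3 simplifies in the wrong order: it removes a variance component before removing a correlation, and its last step has nothing to act on under the stated code. If a between-subject slope SD of about 0.005 ms per ng/mL is dropped, the nominal 90% CI at Cmax covers about 76-83%; with slope variance near zero it covers close to 90%.

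For the primary model the gap is an open, unordered list whose named members carry one variance. The one-sided error at a timepoint with SD 8 or 9 ms against a pooled 7 ms is about 7% or 9-10%, with mild conservatism at quieter timepoints.

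All variance components, timepoint SDs and the shape of the concentration profile are assumptions. The documents do not support saying that the primary conclusion is biased, that a single variance is mandated, or that both random terms are likely to be lost.

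**What to change.** **SAP 6.3.** After rescaling, refit with uncorrelated random intercept and slope (TYPE=VC). Drop the slope only if its variance is estimated as zero or that model also fails. Keep the subject intercept throughout. Delete the sentence that tries other matrices only once the random terms are gone. Zero correlation is itself an assumption, but a milder one than zero slope variance.

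**SAP 6.1 and Protocol 8.3.3.2.** Name heterogeneous structures first, in a fixed order: for example TYPE=CSH, then another heterogeneous form such as TOEPH or ARH(1). Report the first that converges. State that these forms ignore the unequal spacing (15 minutes up to 12 hours between timepoints); they repair the variances, not the spacing.

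**Cost.** Wording only. If a fallback is used, intervals become slightly wider at some timepoints and possibly at Cmax. If the planned models converge, nothing changes.
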